5.2.2 Exclusion Criteria

1. Diagnosis of active or recurrent cancer, or less than 3 months at the time of initial evaluation from the completion of chemotherapy, radiation therapy or primary surgery for the treatment of cancer.
2. Active skin or limb infection/inflammatory disease (acute cellulitis, or other uncontrolled skin or untreated inflammatory skin disease)
3. Acute thrombophlebitis (in last 2 months)
4. Pulmonary embolism within the previous 6 months
5. Deep Vein Thrombosis (DVT) within the previous 3 months
6. Severe peripheral artery disease (critical limb ischemia including ischemic rest pain, arterial wounds, or gangrene)
7. Pulmonary edema
8. Heart failure (acute pulmonary edema, decompensated acute heart failure)
9. Patients with poorly controlled asthma
10. Previous use of the study PCD

11. Currently using multi-layer bandaging (MLB) unless bandages can be removed for limb circumference measurements
12. Pregnant women or women of childbearing potential not on contraception
13. Any condition where increased venous and lymphatic return is undesirable
14. Currently participating in another medical device or drug clinical trial
15. Signs of noncompliance at the week 4 visit, including: using the device less than 3 times per week and/or not attending the scheduled visit

5.2.3 Subject Withdrawal or Early Termination

Subjects will exit the study if they meet any of the following criteria:

- Subject death
- Subject voluntarily withdraws
- Subject acquires one or more of the exclusion criteria whereby the investigator deems study discontinuation a necessity
 - If subject acquires an infection, they may be treated for the infection and continue in the trial at the investigator’s discretion. Detailed information regarding the infection, nature, treatment, and duration will be recorded.
- Subject diary shows an unwillingness to remain partially compliant or compliant with prescribed care (subject will be considered a screen failure if he or she uses the device <3 times per week on average at the Week 4 visit).

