5.1.2 Secondary Endpoints

The secondary endpoints for this study will compare changes after 12 and 52 weeks of treatment to baseline for the following:

- Limb circumference
- Skin evaluation

In addition, changes after 24 and 52 weeks of treatment to baseline for the following parameter:

- QoL

To assess Flexitouch compliance, subjects will be categorized as noncompliant, partially compliant, or compliant (Table 1). Primary and secondary outcomes will then be compared across the defined compliance categories.

Table 1. Compliance Category Definitions

Compliance Category	Definition
Noncompliant	Prescribed care followed an average of 0-2 days per week.
Partially Compliance	Prescribed care followed an average of 3-4 days per week.
Compliant	Prescribed care followed an average of 5-7 days per week.

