7.10 Flexitouch Compliance Assessment & Subject Diary

At each phone call and clinic visit, subject compliance will be assessed by collecting the following information:

- Days Flexitouch used in past week
- Days compression garments used in past week
- Difficulty in following treatment
- Difficulty in putting on Flexitouch garments
- Difficulty using Flexitouch controller
- Pain or discomfort experienced when using Flexitouch
- Position treatment being done in

If the subject reports difficulty following treatment, putting on the Flexitouch garment, difficulty using the Flexitouch controller, or is experiencing pain or discomfort when using Flexitouch, the site may refer the subject to Tactile Medical clinical services for assistance in addressing the issue(s).

In addition, the subjects will be provided with a Subject Diary at their Screening/Baseline visit and be instructed to begin completing the diary when they start using their device after their training visit. The subject will be asked to keep a daily record of their use of Flexitouch, Actitouch (if prescribed), and compression stockings. (Appendix C) Subjects should bring their diary into each study visit for review and collection.

If the subject is noncompliant or partially compliant in device use, (see Table 1), the site should identify barriers to compliance and determine if additional device training by the site or Tactile personnel is warranted. If noncompliance continues, the Investigator may initiate the subject's withdrawal from the study.

At the 4 week in-clinic follow-up visit, if a subject is not using their Flexitouch an average of 3 times per week, they will be considered a screen failure.

If the subject experiences a complication (e.g., active infection, DVT) that requires temporary discontinuation of device use and 4 weeks of continuous treatment is not possible before the final in-clinic visit takes place, the subject should be withdrawn from the study.

Additionally, a device history log may be downloaded periodically from Flexitouch Plus units.

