13.2 Determination of Sample Size

The study is planned to have up to 300 subjects enrolled. Each subject will undergo treatment as prescribed, using the Flexitouch system or Flexitouch Plus. This sample of convenience was selected based on the investigator's previous pilot study and experience with this patient population.

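### The low-use exit provisions in 5.2.3 and 7.10 conflict, and they deplete and select the Noncompliant class that 5.1.2 sets out to compare

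*Combined protocol and SAP*

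**What the plan says.** Table 1 in section 5.1.2 defines three classes: Noncompliant ("Prescribed care followed an average of 0-2 days per week"), Partially compliant ("Prescribed care followed an average of 3-4 days per week") and Compliant ("Prescribed care followed an average of 5-7 days per week"). The section then says: "Primary and secondary outcomes will then be compared across the defined compliance categories". It does not state the period over which the average is taken. Section 4.0 also lists Flexitouch compliance among the things the study will assess.

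Two passages deal with low use after Week 4. The Week 4 screen failure is a separate rule and is not the subject of this point.

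- Section 5.2.3 lists the grounds on which subjects leave the study, in mandatory wording. One is "Subject diary shows an unwillingness to remain partially compliant or compliant with prescribed care". It gives no threshold, look-back period or end date.
- Section 7.10 says the site should find out what is getting in the way and consider more training. Only then comes withdrawal, as an option: "If noncompliance continues, the Investigator may initiate the" withdrawal of the subject.

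Under 6.4 and the schedule in 7.13, diaries are collected at the clinic visits at Weeks 4, 8, 12, 24 and 52. Quality of life is measured at baseline and at Weeks 12, 24 and 52. There is no exit visit. Section 13.1 does not say how subjects who leave are classed or analysed. On size, 13.2 says "The study is planned to have up to 300 subjects enrolled" and "This sample of convenience was selected based on the investigator's previous pilot study and experience with this patient population".

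**The concern.** Section 5.2.3 uses Table 1's own labels. A subject who is no longer partially compliant or compliant is, in those terms, Noncompliant. Lasting membership of one of the three analysis classes is thus close to being a ground for leaving the study.

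The study has a single arm, so the comparison by compliance is its only internal contrast by amount of use, and the Noncompliant class shows what happens with little use. If low users leave before their later outcomes, the class shrinks. Those who remain are not a fair sample of low users: they are the ones whose site chose to keep them, or whose use fell late. Because 5.2.3 and 7.10 differ in obligation, the selection can differ from site to site. The compliance distribution is affected in the same way, because its lower end is partly cut off by rule.

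**Working it through.** The plan gives no figure to reproduce: 13.2 states no effect size, standard deviation, power or dropout rate. The check therefore has three parts.

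**1. The two passages side by side**

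| | 5.2.3 | 7.10 |
|---|---|---|
| Trigger | Diary shows unwillingness | Noncompliance continues |
| Step before exit | None stated | Address obstacles, consider retraining |
| Force | Mandatory | Investigator's option |

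One subject can fall under both, with different results.

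**2. When exit can precede an outcome**

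Table 1 gives no averaging period, so assume days are averaged from Day 0. Assume also that device use stands in for prescribed care, which is what Table 1 counts. With a days per week in Weeks 1 to 4 and b days per week afterwards, the average at Week T is (4a + (T − 4)b)/T.

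Low use that shows before the Week 12 outcome:

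- a = 3, b = 0: Week 8 gives 12/8 = 1.5; Week 12 would give 12/12 = 1.0.
- a = 3, b = 1: Week 8 gives 16/8 = 2.0; Week 12 would give 20/12 = 1.67.

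Both subjects pass the Week 4 rule and are Noncompliant at the Week 8 diary collection. They can be removed before the Week 12 primary outcome.

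Low use that first shows at the outcome visit itself:

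- 3 days per week to Week 8, then 0: (24 + 0)/12 = 2.0 at Week 12.
- 3 days per week to Week 12, then 1: (36 + 12)/24 = 48/24 = 2.0 at Week 24.
- 3 days per week to Week 24, then 1: (72 + 28)/52 = 100/52 = 1.92 at Week 52.

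These subjects are Noncompliant when the outcome is taken, and no earlier diary showed low use. The first can still be removed before Weeks 24 and 52, and the second before Week 52. Anyone who exits before Week 52 has an incomplete utilization count for the comparison with the preceding year in 5.1.1.

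**3. Size, on assumed rates**

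Suppose 300 subjects pass Week 4, a share p become low users, and a fraction q of these are withdrawn before the outcome, with no other dropout. The number left in the class is n = 300p(1 − q), and m = 300(1 − p) are in the other classes. The detectable standardized difference between the low users who remain and all others (two-sided 0.05, 80% power, normal approximation) is (1.96 + 0.84) × √(1/n + 1/m).

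| Low users | q = 0 | q = 50% | q = 80% | q = 90% |
|---|---|---|---|---|
| 15 (5%) | 15; 0.74 SD | 7.5; 1.04 SD | 3; 1.63 SD | 1.5; 2.29 SD |
| 30 (10%) | 30; 0.54 SD | 15; 0.74 SD | 6; 1.16 SD | 3; 1.63 SD |
| 60 (20%) | 60; 0.40 SD | 30; 0.54 SD | 12; 0.83 SD | 6; 1.16 SD |

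Each cell shows the expected number left and the detectable difference. For example, with 30 low users and half withdrawn, n = 15 and m = 270, and 2.80 × √(1/15 + 1/270) = 0.74. Withdrawing 50% to 90% leaves about 2 to 30 subjects across the table. Only q = 100% leaves none.

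**The case against.** A reader might infer that the exit rule empties the Noncompliant class, so that the three-class comparison cannot be made at all, or that a subject can enter the class only if a site ignores the rule. The documents do not support this. Section 5.2.3 acts on the diary, and the diary is collected at the same visits at which outcomes are measured, so low use can come to light together with the outcome. Section 7.10 puts support first and lets noncompliant subjects stay. Unwillingness is a judgement, not a count. Section 5.2.3 also lets subjects with an infection continue at the investigator's discretion, and 7.10 allows for temporary interruption of device use, so some subjects can have low averages without being unwilling. Finally, the Week 4 rule counts device use while Table 1 counts prescribed care, so a subject can pass one and still be Noncompliant on the other. All of this stands.

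It can also be said that the comparison is secondary, has no stated power and would be confounded by whatever drives compliance even if every subject stayed. That is true, but it does not excuse a further selection that the plan itself introduces. Likewise, nothing says that data collected before exit are discarded, so use up to exit could enter the compliance distribution. The plan does not say that it will, and later outcomes would still be missing.

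**Conclusion.** The concern holds in this form: sections 5.2.3 and 7.10 contradict each other on whether exit for low use is mandatory, and both act on the behaviour that defines an analysis class. The contradiction is plain from the text and needs no assumption. That low users can be lost before later outcomes follows from the visit schedule. That the class is likely to be small and selected by site practice is a reasonable inference.

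How small cannot be known from the documents, because they give neither the share of low users nor the share withdrawn. On the assumed 30 low users of 300, withdrawing 50% to 90% leaves 15 to 3, and the detectable difference rises from 0.54 SD with none withdrawn to between 0.74 and 1.63 SD. These figures illustrate loss of precision only. The bias from selective exit is separate, and a larger sample would not remove it.

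**What to change.** Reconcile 5.2.3 with 7.10 so that low use after Week 4 does not by itself end study follow-up. These subjects would keep attending the remaining scheduled visits and calls, with their use recorded as it is. Voluntary withdrawal remains open and device care is unchanged; the amendment concerns data collection only.

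If the sponsor keeps the exit rule, the two passages must still be made to agree. Section 5.1.2 should then be restated as a comparison of Partially compliant with Compliant subjects, and the number and timing of low-use exits should be reported alongside the compliance and outcome results.

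In either case, state the averaging period for Table 1 and how subjects who leave early are classed and analysed.

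The cost is a wording amendment, reviewed and approved as section 12.0 requires. The visits and calls are already in the schedule in 7.13. The downside is that some low users will attend poorly, and the overall mean change may look slightly less favourable once they are kept in.

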5.3 Dosage and Rationale

Study subjects will be instructed to conduct LE treatment as prescribed by their physician. They will also be instructed to wear clinically appropriate compression garments and participate in proper skin care as part of their routine care.

5.4 Study Timetable

Table 2. Study Timetable

	1-6 months	7-12 months	12-24 months	24-36 months
IRB Review	X			
Enrollment	X	X	X	X
Treatment	X	X	X	X
Data Entry	X	X	X	X
Data Analysis				X
Manuscript Draft				X
Publication				2021

6.0 Study Visit Summaries

The sections below provide a summary of procedures at each study visit. For further detail for each procedure, please refer to section 7 (Study Procedures) of the protocol.

In the event a patient is unwilling or unable to attend a scheduled Follow-Up Visit, the site will have the discretion to offer a home visit to the patient.

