5.1 Study Endpoints

5.1.1 Primary Endpoints

The following primary endpoints for this study will compare changes after 12 weeks of treatment to baseline for the following parameters:

- QoL
- Lymphedema symptoms

In addition, the number of occurrences after 52 weeks of treatment will be compared to the number of occurrences in the year preceding treatment for the following variable:

- Lymphedema and venous related health care utilization

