6.2 Week 0/Training

- The subject will receive the Flexitouch system or Flexitouch Plus and be instructed on use from a Tactile Medical trainer. Device treatment will commence following the visit from the trainer.

6.3 Weeks 1 (+7 days), 18, 32, & 40 (± 14 days) Follow-up Phone Calls

- Prescribed care and treatment protocol
- Medication review
- Flexitouch compliance assessment
- Complication, adverse event, and device observation assessment

6.4 Weeks 4, 8, 12 (± 7 days), 24, and 52 (± 14 days) In-Clinic Follow-Up Visit(s)

- Weight (kg)
- Skin assessment
- Limb circumference
- Photographs (Leg)
- Prescribed care and treatment protocol
- Medication review
- QoL Questionnaires (Weeks 12, 24, and 52 only)
 - LYMQOL
 - SF-36
- Subject diary collection
- Flexitouch compliance assessment
- Complication, adverse event, and device observation assessment

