7.13 Study Schedule of Activities

Assessments	Screening/Baseline	Training / Day 0	Week 1 (Phone Call)	Week 4	Week 8	Week 12	Week 18 (Phone call)	Week 24	Week 32 (Phone call)	Week 40 (Phone call)	Week 52
Visit Window	N/A	N/A	+7 Days	±7 Days	±7 days	±7 days	±14 days	±14days	±14 days	±14 days	±14 days
Informed Consent	X										
Inclusion/Exclusion	X										
Demographics	X										
Medical History/Status	X ¹										
Vital Signs² (Height, Weight)	X			X	X	X		X			X
Skin Assessment	X			X	X	X		X			X
Limb Circumference	X			X	X	X		X			X
Photograph (Leg)	X			X	X	X		X			X
Prescribed Care & Treatment Protocol	X		X	X	X	X	X	X	X	X	X
Medication Review	X		X	X	X	X	X	X	X	X	X
Quality of Life Assessments	X					X		X			X
Subject Diary	X ³			X	X	X		X			X
Flexitouch Compliance			X	X	X	X	X	X	X	X	X
HCU, Adverse Events, & Device Observations			X	X	X	X	X	X	X	X	X
Flexitouch Training		X									

¹Includes Lymphedema History

²Height and weight collected at Screening/Baseline, weight collected at all subsequent visits

³Dispense and train subject on subject diary completion

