17.0 Appendices

Appendix A: Lymphedema Quality of Life Tool (LYMQOL)

Appendix B: SF-36 Health Survey v.2 (SF-36)

Appendix C: Subject Diary

Appendix A: Lymphedema Quality of Life Tool (LYMQOL)

LYMQOL (Source Document)

Assessment of Quality of Life Changes on Lower Extremity Lymphedema Patients using an Advanced Pneumatic Compression Device at Home Protocol #5010

Subject ID: _____ - _____

Visit Date: ____/____/____
(ddMMyyyy)

LYMQOL LEG
Lymphoedema Quality of Life Tool

This questionnaire has been designed and validated for patients with chronic oedema/ lymphoedema of one or both legs to measure quality of life. Please tick the box that best describes how you feel about each of the questions.

If any of the items are not applicable to you, please write N/A in the relevant answer box(es)

(Q1) How much does your swollen leg affect the following activities?	Not at all	A little	Quite a bit	A lot
a) your walking				
b) your ability to bend, e.g. to tie shoelaces or cut toenails				
c) your ability to stand.				
d) your ability to get up from a chair.				
e) your occupation				
f) your ability to do housework				

	Not at all	A little	Quite a bit	A lot
(Q2) Does the swelling affect your leisure activities/ social life?				

Please give examples of this

.....

	Not at all	A little	Quite a bit	A lot
(Q3) How much do you have to depend on other people?				
(Q4) How much do you feel the swelling affects your appearance?				
(Q5) How much difficulty do you have finding clothes to fit?				
(Q6) How much difficulty do you have finding clothes you would like to wear?				
(Q7) Do you have difficulty finding shoes to fit?				
(Q8) Do you have difficulty finding socks/ tights/ stockings to fit?				
(Q9) Does the swelling affect how you feel about yourself?				
(Q10) Does it affect your relationships with other people?				
(Q11) Does your lymphoedema cause you pain?				

LYMQOL (Source Document)

Assessment of Quality of Life Changes on Lower Extremity Lymphedema Patients using an Advanced Pneumatic Compression Device at Home Protocol #5010

Subject ID: _____ - _____

	Not at all	A little	Quite a bit	A lot
(Q12) Do you have any numbness in your swollen leg(s)?				
(Q13) Do you have any feelings of "pins & needles" or tingling in your swollen leg(s)				
(Q14) Does (do) your swollen leg(s) feel weak?				
(Q15) Does (do) your swollen leg(s) feel heavy?				

In the past week....

	Not at all	A little	Quite a bit	A lot
(Q16) Have you had trouble sleeping?				

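### For a subject still in the study who misses Week 12, 24 or 52, QoL is collected only if the site chooses to offer a home visit; a required remote route would reduce selective missingness

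*Combined protocol and SAP*

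**What the plan says.** Section 5.1.1 makes QoL and lymphedema symptoms primary at Week 12: the endpoints "will compare changes after 12 weeks of treatment to baseline for the following parameters". Section 5.1.2 makes the later QoL comparisons secondary: "changes after 24 and 52 weeks of treatment to baseline for the following parameter".

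Section 6.4 places the forms at three in-clinic follow-up visits: "QoL Questionnaires (Weeks 12, 24, and 52 only". In the section 7.13 schedule, the row "Quality of Life Assessments" is marked at baseline and at those three visits and nowhere else. Section 6.3, "Weeks 1 (+7 days), 18, 32, & 40 (± 14 days) Follow-up Phone Calls", lists no QoL item.

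Section 6.0 foresees missed visits. It begins "In the event a patient is unwilling or unable to attend a scheduled Follow-Up Visit" and its whole response is that "the site will have the discretion to offer a home visit to the patient". Neither section 6 nor section 7.9 describes completion by post, by phone or at home without a visit.

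The LYMQOL in Appendix A addresses the patient directly: "Please tick the box that best describes how you feel about each of the questions". The SF-36 in Appendix B is worded in the same way. Section 7.11 has health care utilization assessed at every phone call and every clinic follow-up visit.

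**The concern.** The home-visit provision is permissive and left to each site of a multi-center study. For a subject who has not withdrawn but does not come to clinic at Week 12, the primary QoL and symptom values exist only if that site offers a visit and the subject accepts it. Two things can then decide who is measured: why the subject stayed away, and how the site uses its discretion. If either is related to the change in QoL, the mean among those measured differs from the mean among all who remain in the study. With one arm and a before-after comparison, no control group with similar losses exists to offset the difference. A QoL value not collected near its time point cannot be recovered later.

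Nothing in either questionnaire needs an examination, so the dependence on attendance looks avoidable.

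**Working it through.** **Step 1: is another route stated?**

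| Item | In clinic | By phone | If the visit is missed |
|---|---|---|---|
| QoL and symptoms, Week 12 (primary) | Yes (6.4, 7.13) | No (6.3, 7.13) | Discretionary home visit (6.0) |
| QoL, Weeks 24 and 52 (secondary) | Yes (6.4, 7.13) | No (6.3, 7.13) | Discretionary home visit (6.0) |
| Health care utilization (primary) | Yes (7.11) | Yes (7.11) | Also asked at the phone contacts |

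Remote collection is thus already accepted for one primary endpoint and not provided for the other two.

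**Step 2: what figures do the documents give?** Section 13.2 gives up to 300 subjects, described as a sample of convenience. It states no SD, effect size, power or dropout, so there is no calculation to reproduce. No attendance rate, reason for absence or outcome by attendance is given. What follows is illustration on assumed inputs.

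**Step 3: bias of the observed mean.** Let *m* be the share of in-study subjects without a form and *d* the mean change in those with a form minus the mean change in those without, in SDs of change. The mean over all in-study subjects is (1 − m) × mean(with) + m × mean(without). The observed mean is mean(with). The difference is

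bias = m × d.

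Assumed ranges: m = 5% to 20%, and d = 0 to 0.5 SD in size, of either sign. For scale, the 95% half-width of a mean change is 1.96/√n. All 300 are taken as still in the study, because no dropout figure is stated.

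| m | No form, of 300 | n with form | 95% half-width (SD) | Bias, d = 0 | Bias, d = ±0.25 | Bias, d = ±0.5 |
|---|---|---|---|---|---|---|
| 5% | 15 | 285 | 0.116 | 0 | ±0.0125 | ±0.025 |
| 10% | 30 | 270 | 0.119 | 0 | ±0.025 | ±0.05 |
| 20% | 60 | 240 | 0.127 | 0 | ±0.05 | ±0.10 |

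With all 300 forms the half-width is 1.96/√300 = 0.113 SD. Precision therefore changes little (0.113 to 0.127 SD). What matters is selection, which a larger sample does not remove. Across this range the bias stays inside the half-width; the worst case is 0.10 against 0.127 SD. At d = 0.5 it would exceed the half-width only from about 26% missing, which is outside the range.

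**Step 4: effect of a remote route.** Suppose half to three quarters of the missed forms are recovered (assumed) and the recovered subjects resemble those still missing. Then m falls from 20% to between 20% × 0.50 = 10% and 20% × 0.25 = 5%. At d = 0.5 the bias falls from 0.10 SD to between 0.05 and 0.025 SD.

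**The case against.** The protocol does provide a mitigation, and it is silent on other routes rather than forbidding them. A site could send the forms today without contradicting the text. That stands: the values are at risk, and the documents do not show that they are lost.

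A reader might infer that the subjects missed are those doing worst, so that the observed improvement is inflated. Section 6.0 covers the unwilling as well as the unable, and an unwilling subject may be doing well or badly. The documents give no basis for a direction.

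A reader might also put total Week 12 loss into the formula; 25% × 0.5 SD, for example, gives 0.125 SD. That total would include deaths, voluntary withdrawals and compliance exits under section 5.2.3, whom a posted form would not reach, and it would ignore home visits that are made. In addition, exclusion criterion 15 removes subjects who do not attend Week 4, so the group due at Week 12 is already selected for attendance. The relevant share is smaller than total loss, and unknown.

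Self-completion is inferred from the wording of the forms. Section 7.9 states no mode, both forms carry a signature line for the person completing them, and the LYMQOL refers queries to the study coordinator. This calls for a stated procedure but does not rule out remote use.

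Finally, section 13 sets no test or success threshold that such a bias could overturn. That limits the weight of the point. It does not remove the case for a cheap safeguard.

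**Conclusion.** The point holds as a low-cost improvement of minor severity. For an in-study subject who does not attend, QoL depends on a discretionary home visit, and no other route is stated. This touches a primary endpoint at Week 12 only. At Weeks 24 and 52 it touches secondary QoL, so it would be wrong to read all three visits as primary data. Health care utilization is not wholly dependent on attendance.

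Missingness may depend on subject status and site practice, with no comparator to offset it. The direction and size of any bias are unknown. The figure of 0 to 0.10 SD, in either direction, rests entirely on the assumed 5% to 20% without a form and the assumed 0 to 0.5 SD difference. It is not an estimate for this trial.

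**What to change.** In sections 6.0 and 6.4, require the following for Weeks 12, 24 and 52:

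- As soon as a subject says they cannot or will not attend, or misses the scheduled appointment, the site sends the unchanged LYMQOL and SF-36 for self-completion and makes a reminder call, whether or not a home visit is offered.
- The aim is completion inside the existing visit window (±7 days at Week 12, ±14 days at Weeks 24 and 52). The trigger should not wait for the window to close, because every posted form would then be out of window.
- The site records completion date, mode and reason for non-attendance.
- Remote forms enter the main comparison. Results are reported with and without remote forms, and with and without out-of-window forms, as a description of sensitivity. This is not a test of mode effect: leaving out remote forms also leaves out the non-attenders, so mode and selection cannot be separated.

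Cost: postage, the effort of sending, tracking and calling, and a few data fields. The downside is a possible small mode effect. No clinic visit or examination is added, and no treatment or withdrawal rule changes.
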